9.1.1.7 Visit 9 (Day 281 [± 7])

A visit window of ± 7 days from the scheduled visit date is permitted, but it is preferred that the visit is performed on the scheduled visit day, where possible.

Information regarding changes to concomitant medications and AEs will be reviewed. Physical examination (including body weight) and vital sign assessments will be performed. Blood samples will be taken for the following:

- Hematology
- Biochemistry

The investigator must assess adherence to the dosing schedule.

The investigator will complete the suicidality assessment.

All GWP42003-P (used and unused) will be collected, and a check of the returned GWP42003-P against usage should be made. Patients will receive sufficient GWP42003-P and a dosing schedule for the following 12 weeks.

Study Code: GWND19002
EudraCT Number: 2019-001605-24
Clinical Protocol V2 18Dec19

9.1.1.8 Visit 11 (Day 456 [± 7]) and Visit 13 (Day 638 [± 7])

Visits 11 and 13 are resupply visits. Patient's taking concomitant valproic acid or whose dose exceeds 15 mg/kg/day will need hepatic monitoring. All other patients do not need to attend in person. A visit window of ± 7 days from the scheduled visit date is permitted, but it is preferred that the visit is performed on the scheduled visit day, where possible.

Information regarding changes to concomitant medications and AEs will be reviewed.

The investigator must assess adherence to the dosing schedule.

All GWP42003-P (used and unused) will be collected, and a check of the returned GWP42003-P against usage should be made. Sufficient GWP42003-P and a dosing schedule will be provided for the following 13 weeks.

Based on [Section 9.1.3](#), assessments may be performed at an unscheduled visit in the event of a safety concern, as deemed necessary by the investigator.

9.1.1.9 Visit 12 (Day 547 [± 7])

A visit window of ± 7 days from the scheduled visit date is permitted, but it is preferred that the visit is performed on the scheduled visit day, where possible.

Information regarding changes to concomitant medications, AEs will be reviewed. Vital sign assessments, physical examination (including body weight), height, and ECG assessments will be performed.

Clinical laboratory samples (urine [where possible] and blood) will be taken for the following:

- Hematology
- Biochemistry
- Dipstick urinalysis (provided urine can be obtained)
- Pregnancy test using a serum sample (as appropriate [[Section 9.2.2](#)])

The investigator will complete suicidality assessment.

The investigator must assess adherence to the dosing schedule.

All GWP42003-P (used and unused) will be collected, and a check of the returned GWP42003-P against usage should be made. Patients will receive sufficient GWP42003-P and a dosing schedule for the following 13 weeks.

Study Code: GWND19002
EudraCT Number: 2019-001605-24
Clinical Protocol V2 18Dec19

9.1.1.10 Visit 15 (Day 739 [+ 7], End of Taper)

A visit window of + 7 days from the scheduled visit date is permitted, but it is preferred that the visit is performed on the scheduled visit day, where possible. This visit marks the end of the taper period.

Information regarding changes to concomitant medications and AEs will be reviewed. Vital sign and suicidality assessments will be performed.

The investigator must assess adherence to the dosing schedule.

All GWP42003-P (used and unused) will be collected, and a check of the returned GWP42003-P against usage should be made.

The following assessments are not required but should be performed if clinically indicated:

- Physical examination (including body weight)
- ECG
- Clinical laboratory samples (urine [where possible] and blood) will be taken for the following:
 - Hematology
 - Biochemistry

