9.1.1.7 Visit 9 (Day 207 [+ 7], End of Taper)

This visit will occur 10 days after the end of treatment (Visit 8). A visit window of + 7 days from the scheduled visit date is permitted, but it is preferred that the visit is performed on the scheduled visit day, where possible. This visit marks the end of the taper period.

Information regarding changes to concomitant medications and AEs will be reviewed. Vital sign assessments will be performed. The investigator must assess adherence to the dosing schedule.

The investigator will complete the suicidality assessment.

Study Code: GWND19002

EudraCT Number: 2019-001605-24

Clinical Protocol V1 09Aug19

All GWP42003-P (used and unused) will be collected, and a check of the returned GWP42003-P against usage should be made.

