Hepatic function monitoring should be carried out within 1 month following increases in GWP42003-P dose or introduction or dose increases of medications that are known to impact liver function. If the concerned change does not occur within 1 month of a scheduled biochemistry assessment, the investigator should perform an additional hepatic monitoring within 1 month of the change.

Transaminase elevations should be medically managed by the investigator either by reducing the GWP42003-P dose as described above or by reducing concomitant medications judged to be causing the elevation (per [Section 8.2](#)). Dose adjustments should be discussed with the GW medical monitor. For potential cases of drug-induced liver injury, see [Section 12.8](#).

At the end of treatment (Visit 14 [Day 729]), the dose of GWP42003-P will be reduced over a 10-day taper period, and patients will enter the 4-week follow-up period.

Patients discontinuing GWP42003-P treatment at any other time should undergo a 10-day taper period (unless continued dosing is inadvisable, e.g., due to an AE). The decision on whether to taper GWP42003-P or not will be left to the investigator's clinical judgment.

Study Code: GWND19002
EudraCT Number: 2019-001605-24
Clinical Protocol V2 18Dec19

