9.1.1.5 Visit 7 (Day 141 [± 7])

A visit window of ± 7 days from the scheduled visit date is permitted, but it is preferred that the visit is performed on the scheduled visit day, where possible.

Information regarding changes to concomitant medications and AEs will be reviewed. The investigator must assess adherence to the dosing schedule.

Study Code: GWND19002
EudraCT Number: 2019-001605-24
Clinical Protocol V2 18Dec19

Vital sign assessments will be performed.

Clinical laboratory samples (urine [where possible] and blood) will be taken for hematology and biochemistry for patients taking concomitant valproic acid, as well as for patients whose dose exceeds 15 mg/kg/day.

The caregiver will complete the RSBQ and Caregiver Assessment of Rett Symptoms.

The Hospital Services Use Questionnaire will be completed via interview.

The investigator will complete CGI-S, CGI-I, and suicidality assessment.

All GWP42003-P (used and unused) will be collected, and a check of the returned GWP42003-P against usage should be made. Patients will receive sufficient GWP42003-P and a dosing schedule for the following 8 weeks.

Based on [Section 9.1.3](#), assessments may be performed at an unscheduled visit in the event of a safety concern, as deemed necessary by the investigator.

9.1.1.6 Visit 8 (Day 197 [± 7]), Visit 10 (Day 365 [± 7]), and Visit 14 (Day 729 [± 7], End of Treatment/Withdrawal Visit)

A visit window of ± 7 days for Visits 8, 10, and 14 from the scheduled visit date is permitted, but it is preferred that the visit is performed on the scheduled visit day, where possible.

The patient should attend a withdrawal visit (Visit 14) as soon as possible after the decision is made to permanently discontinue GWP42003-P.

Information regarding changes to concomitant medications, AEs, and menstruation cycle (where applicable) will be reviewed. Vital sign assessments, physical examination (including body weight), height, and ECG assessments will be performed.

Clinical laboratory samples (urine [where possible] and blood) will be taken for the following:

- Hematology
- Biochemistry
- Dipstick urinalysis (provided urine can be obtained)
- Pregnancy test using a serum sample (as appropriate [[Section 9.2.2](#)])
- Determination of serum IGF-1 levels ([Section 9.2.9](#))

Study Code: GWND19002

EudraCT Number: 2019-001605-24

Clinical Protocol V2 18Dec19

The caregiver will complete the RSBQ, CSHQ, SF-36, CHQ-PF50, and Caregiver Assessment of Rett Symptoms.

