The Hospital Services Use Questionnaire will be completed via interview.

The Tanner Stage will be recorded (where appropriate).

The investigator will complete MBA-9, CGI-S, CGI-I, and suicidality assessment.

The investigator must assess adherence to the dosing schedule. All GWP42003-P (used and unused) will be collected, and a check of the returned GWP42003-P against usage should be made. Patients will receive sufficient GWP42003-P and a dosing schedule for the period until the next scheduled Visit.

Based on [Section 9.1.3](#), assessments may be performed at an unscheduled visit in the event of a safety concern, as deemed necessary by the investigator.

Visit 14 only: Patients will receive sufficient GWP42003-P for the 10-day taper period, as applicable. For patients who discontinue GWP42003-P early, the taper period should start at the time the decision is made to discontinue, unless tapering the dose of GWP42003-P is inadvisable (e.g., continued dosing is not possible due to an AE). For patients who discontinue GWP42003-P early, the decision on whether or not to taper GWP42003-P will be left to the investigator's clinical judgment.

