9.1.2 Dipstick urinalysis (provided urine can be obtained)Telephone Visits

9.1.2.1 Visits 2 (Day 8 [± 3]) and 3 (Day 15 [± 3])

A visit window of ± 3 days from the scheduled visit date is permitted, but it is preferred that the visit is performed on the scheduled visit day, where possible.

Telephone visits will be conducted by a center nurse (the center investigator only needs to be involved if necessary, e.g., if any concerns are raised during the call). Information regarding changes to concomitant medications and AEs will be reviewed. The center (the nurse and, if necessary, the investigator) must assess adherence to the dosing schedule.

Study Code: GWND19002
EudraCT Number: 2019-001605-24
Clinical Protocol V2 18Dec19

9.1.2.2 Visit 16 (28 days after last dose IMP [+ 7], Follow-up, End of Trial)

A visit window of + 7 days from the scheduled visit date is permitted, but it is preferred that the visit is performed on the scheduled visit day, where possible. This visit marks the end of the trial.

Visit 16 constitutes the last scheduled safety follow-up. The purpose of the visit is to ascertain the status of AEs continuing after the cessation of GWP42003-P or any new AEs commencing after discontinuation. All causally related AEs that result in a patient's early termination from the trial or are present at the end of the trial should be followed up until a satisfactory resolution occurs, i.e., until the AE resolves or is considered clinically insignificant, or until the investigator is satisfied that the AE is not related to GWP42003-P and needs no further investigation. Information regarding changes to concomitant medications will be reviewed.

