6.1 Statistical Definitions and Algorithms

6.1.1 Conventions for treatment/visit naming

In all tables, listings and figures, the treatment arms will be referred to and labelled as per [Table 2](#).

Table 2 Study treatments

Endpoint	RCT Treatment	Actual Treatment	Protocol/Annex	Treatment Label (Table column/Figure legend)	Sorting order in listings, column order in tables
All	Double-Blind Treatment GWP42003-P different dosing	GWP42003-P, at different dosing	Enrolled under Protocol	Double Blind Treatment: GWP42003-P Enrolled Under Protocol	1
All	Double-Blind Treatment GWP42003-P different dosing	GWP42003-P, at different dosing	Enrolled under Annex	Double Blind Treatment: GWP42003-P Enrolled Under Annex	2
All	Double-Blind Treatment Placebo different dosing	GWP42003-P, at different dosing	Enrolled under Protocol	Double Blind Treatment: Placebo Enrolled Under Protocol	3
All	Double-Blind Treatment Placebo different dosing	GWP42003-P, at different dosing	Enrolled under Annex	Double Blind Treatment: Placebo Enrolled Under Annex	4

In all tables, listings and figures, the study visits will be referred to and labelled as per [Table 3](#).

Table 3 Study Visits

Actual Visit	Visit Label
Baseline (last record before 1 st IMP administration during lead-in trial)	RCT Baseline
Baseline (Assessment at extension Visit 1)	OLE Baseline
Visit 1: Day 1	Day 1
Visit 2: Day 8 Telephone Call	Day 8 TC
Visit 3: Day 15 Telephone Call	Day 15 TC
Visit 4: Day 29	Day 29
Visit 5: Day 57	Day 57
Visit 6: Day 85	Day 85
Visit 7: Day 141	Day 141
Visit 8: Day 197	Day 197
Visit 9: Day 281	Day 281
Visit 10: Day 365	Day 365
Visit 12: Day 547	Day 547
Visit 14: Day 729 or withdrawal	End of Treatment
Visit 15: Day 739 (end of taper)	End of Taper
Visit 16: Day 767	Follow-up

No derivation will be used for visits; data will be tabulated and listed according to the visit it was recorded under in eCRF.

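### Visit 15 (End of Taper) is fixed at Day 739 (+7) instead of being timed from the taper, so it can fall up to 14 days after the last dose or, on its preferred day, up to 7 days before it

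*Protocol*

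**What the plan says.** All protocol references are to V2 (18 December 2019) unless stated.

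- **Visit 14.** The heading of Section 9.1.1.6 includes "Visit 14 (Day 729 [± 7], End of Treatment/Withdrawal Visit", so a completer may be seen on Days 722 to 736. An early withdrawal attends the same visit whenever treatment is stopped.
- **Taper.** Section 8.1.2: "At the end of treatment (Visit 14 [Day 729]), the dose of GWP42003-P will be reduced over a 10-day taper period". The supply is handed out at Visit 14 (Section 9.1.1.6): "Patients will receive sufficient GWP42003-P for the 10-day taper period, as applicable".
- **Visit 15.** Section 9.1.1.10, headed "Visit 15 (Day 739 [+ 7], End of Taper", gives Day 739 with a plus-only window: "A visit window of + 7 days from the scheduled visit date is permitted". It prefers the scheduled day where that can be done, describes the visit as closing the taper, and has all used and unused drug collected. Appendix 1 repeats 739 (+7).
- **Order of events.** The synopsis and Sections 4.1 and 10 put Visit 15 after the taper, without a number of days.
- **Visit 16.** Section 9.1.2.2 is headed "Visit 16 (28 days after last dose IMP [+ 7], Follow-up, End of Trial". Appendix 1 shows Day 767 (+7) in the column heading, but its footnote c, repeated under SAP Table 1, ties the follow-up to four weeks after the last dose.
- **SAP.** Table 3 lists "Visit 15: Day 739 (end of taper" under the label End of Taper. Section 6.1.1 rules out any visit derivation. Section 9.3.1 summarizes vital signs at Visit 15 with change from both baselines, and Section 9.3.4 summarizes suicidality by visit. Section 7.4 has the final taper dose date recorded at the end-of-taper visit.

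**The concern.** The taper moves with Visit 14 and the Visit 15 window does not. The protocol states an intention (a visit at the end of the taper) and a window that, taken literally, cannot deliver it for every permitted Visit 14 date.

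Two things are at stake. First, Visit 15 is the only scheduled in-person assessment after the taper starts, because Visit 16 is by telephone. Its vital-sign and suicidality summaries could mix patients still tapering with patients up to two weeks off drug, all labelled End of Taper. Second, drug is collected at Visit 15, daily dose confirmation runs only to Visit 15 (Section 9.2.11), and the final dose date is recorded there. If the visit is held before the taper is complete, drug return conflicts with the stated taper and the final dose date has not yet occurred.

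**Working it through.** **Inputs.** Visit 14: Days 722 to 736 (Section 9.1.1.6). Taper: 10 days from Visit 14 (Section 8.1.2). Visit 15: Days 739 to 746 (Section 9.1.1.10 and Appendix 1).

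**The plan's own figures.** 729 + 10 = 739 and 739 + 28 = 767. Both nominal days reproduce, and together they imply that the last taper dose falls on Visit 14 + 10.

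**Offset of Visit 15 from the end of the taper.** Offset = Visit 15 − (Visit 14 + 10). With Visit 14 on Day 729 + k, k from −7 to +7, the offset runs from −k (window opens) to 7 − k (window closes).

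| Visit 14 | Taper ends | Offset on Day 739 (preferred) | Offset on Day 746 (window closes) |
|---|---|---|---|
| 722 | 732 | +7 | +14 |
| 728 | 738 | +1 | +8 |
| 729 | 739 | 0 | +7 |
| 730 | 740 | −1 | +6 |
| 736 | 746 | −7 | 0 |

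- *Visit 14 on Days 722 to 728.* The taper ends on Days 732 to 738, before the window opens. There is no minus window, so a visit on the day the taper ends would be out of window. The permitted offset reaches +14 days.
- *Visit 14 on Days 730 to 736.* The taper ends on Days 740 to 746, always inside the window. A visit at or after the end of the taper is therefore possible in window for every one of these patients, but the preferred day is 1 to 7 days too early. With Visit 14 on Day 736, only Day 746 is both in window and not before the end of the taper.
- *Gap from Visit 14 to Visit 15.* 739 − 736 = 3 days to 746 − 722 = 24 days, against a 10-day taper.

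**Sensitivity to day counting.** With the last dose on Visit 14 + 9 the range is −6 to +15 days; on Visit 14 + 8 it is −5 to +16. The conclusion does not change.

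**Comparison with a moving anchor.** If Visit 15 = Visit 14 + 10 + w, with w from 0 to 7, the offset is w: 0 to 7 days for every Visit 14 date (1 to 8 if the last dose is on Visit 14 + 9).

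**Early withdrawal.** Visit 14 and the taper can fall on any study day, so Day 739 locates nothing. Section 10 asks those who taper to return for Visit 15 but gives no interval.

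**The case against.** The case for leaving the text alone is that the intent is plain. Several sections put the taper first and Visit 15 after it, drug collection at Visit 15 presupposes a finished taper, and the preference for Day 739 applies only where possible. A sensible site would book the visit for the end of the taper. The final dose date is collected, so time off drug can be recovered, and all reporting is descriptive. This stands as a limit on the impact. It does not remove the conflict: the stated window still excludes the end of the taper when Visit 14 is early, and the SAP does not plan to use the recovered interval.

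Four stronger readings are tempting but not supported.

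- *That late Visit 14 patients are forced into a mid-taper visit.* They are not; the +7 window always contains the end of their taper. Only the preferred day conflicts.
- *That Visit 16 has two competing rules.* Section 9.1.2.2 and footnote c both use the last dose. Day 767 in the column heading and in SAP Table 3 is the nominal 739 + 28.
- *That a known share of completers is affected.* This would need a distribution of Visit 14 dates. The documents give none, and they prefer the scheduled day.
- *That V2 deliberately dropped an anchor.* V1 Section 9.1.1.7 did say "This visit will occur 10 days after the end of treatment (Visit 8". V2 removed similar sentences from the other visits too, which looks like general editing.

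**Conclusion.** The point holds as a timing conflict of limited reach. Read literally, V2 lets Visit 15 fall from 7 days before to 14 days after the last taper dose. The late end arises when Visit 14 is early, where the window excludes the end of the taper. The early end arises when Visit 14 is late, where only the preferred day conflicts. For early withdrawals the protocol gives no usable day at all.

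The exact 7 and 14 days assume that the last dose is on Visit 14 + 10, as Days 739 and 767 imply; other counts move both ends by 1 or 2 days. How many patients are affected is unknown. SAP Section 1 says the extension was stopped prematurely, while Section 9.5 says entrants complete it per protocol and annex.

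A reader might infer that the long-term safety results are compromised. They are not: the consequence is confined to the End of Taper summaries and drug return. The protocol's own change summaries for vital signs and laboratory data (Sections 13.6.2.3 and 13.6.2.4) run to end of treatment, not to Visit 15.

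**What to change.** - **Protocol.** Reconcile Section 9.1.1.10 and Appendix 1 with Sections 4.1, 8.1.2 and 10, so that Visit 15 is timed from the actual start or end of the taper, for early withdrawals as well as completers. Show Day 739 as nominal only. Likewise mark Day 767 as nominal, since Section 9.1.2.2 and footnote c already time Visit 16 from the last dose. Nothing in this changes the dose or the taper.
- **SAP.** Make the same labelling change in Tables 1 and 3. Derive days from the recorded final dose to Visit 15, and identify on-taper values separately in the End of Taper vital-sign and suicidality summaries.

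The cost is one sentence in the protocol, relabelled schedule columns, and one derived variable built from a date that Section 7.4 of the SAP already has collected. If the protocol can no longer be amended, the SAP step alone would make the End of Taper summaries interpretable.

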9.1.2 Dipstick urinalysis (provided urine can be obtained)Telephone Visits

9.1.2.1 Visits 2 (Day 8 [± 3]) and 3 (Day 15 [± 3])

A visit window of ± 3 days from the scheduled visit date is permitted, but it is preferred that the visit is performed on the scheduled visit day, where possible.

Telephone visits will be conducted by a center nurse (the center investigator only needs to be involved if necessary, e.g., if any concerns are raised during the call). Information regarding changes to concomitant medications and AEs will be reviewed. The center (the nurse and, if necessary, the investigator) must assess adherence to the dosing schedule.

Study Code: GWND19002
EudraCT Number: 2019-001605-24
Clinical Protocol V2 18Dec19

9.1.2.2 Visit 16 (28 days after last dose IMP [+ 7], Follow-up, End of Trial)

A visit window of + 7 days from the scheduled visit date is permitted, but it is preferred that the visit is performed on the scheduled visit day, where possible. This visit marks the end of the trial.

Visit 16 constitutes the last scheduled safety follow-up. The purpose of the visit is to ascertain the status of AEs continuing after the cessation of GWP42003-P or any new AEs commencing after discontinuation. All causally related AEs that result in a patient's early termination from the trial or are present at the end of the trial should be followed up until a satisfactory resolution occurs, i.e., until the AE resolves or is considered clinically insignificant, or until the investigator is satisfied that the AE is not related to GWP42003-P and needs no further investigation. Information regarding changes to concomitant medications will be reviewed.

9.1.3 Unscheduled Visits

Unscheduled visits and assessments may be performed in the event of a safety concern, as deemed necessary by the investigator. Data from any unscheduled visits should be reported on the unscheduled visits eCRF.

9.1.4 End of Trial

The end of trial is defined as last patient last visit/telephone call.

9.2 Trial Procedure Listing

9.2.1 Informed Consent/Assent

The parent(s)/legal representative of all patients in the trial must personally sign and date the IRB/IEC-approved informed consent form (ICF) before any trial-specific procedures are performed or any patient-related data are recorded for the trial. The nominated caregiver will be asked to consent to complete the QoL questionnaires.

In cases where the patient possesses adequate understanding in the opinion of the investigator, assent will be taken along with parent(s)/legal representative consent, using IRB/IEC-approved assent forms. If appropriate, prior to signing, the assent form will be read to the patient, and the patient will be given the opportunity to ask questions and discuss with their parent(s)/legal representative. If appropriate, the patient must personally sign and date the assent form. Patients who cannot write can give consent/assent by "making their mark" on the assent form (e.g., writing an "X"). If the

Study Code: GWND19002
EudraCT Number: 2019-001605-24
Clinical Protocol V2 18Dec19

patient possesses adequate understanding but is not physically able to sign, an impartial witness should be present during the entire assent discussion and should sign and personally date the assent form. By signing, the witness attests that the information in the assent form and any other written information were accurately explained to and apparently understood by the patient and that assent was freely given by the patient. Assent is defined as the minor's permission or affirmative agreement to participate in the trial. If a minor who is capable of forming an opinion and assessing the information provided makes an explicit wish to refuse participation in or to be withdrawn from the clinical trial at any time, this wish must be considered by the investigator. Given the severity of the condition, it is expected that the majority of patients will have an insufficient level of understanding of what is proposed, in which case solely parent(s)/legal representative consent will be sought. All decisions made by the investigator relating to a patient's level of understanding and ability to provide assent must be documented in the patient's medical records.

GW Research Ltd requires a physician to be present for consent and assent and to also sign the consent and assent forms. The original signed informed consent/assent forms should be retained, and a copy should be provided to the patient and/or parent(s)/legal representative. Patients' parent(s)/legal representatives will be given the option of being informed about the summary outcome and results of the trial as part of the ICF. For further details, see [Section 15.2](#).

